5.6. Solicited Safety Set

The Solicited Safety Set consists of randomized participants who received at least one dose of IP and contributed any solicited AR data, i.e. have at least one post-baseline solicited safety (eDiary) assessment. The Solicited Safety Set will be used for the analyses of solicited ARs and participants will be included in the treatment group corresponding to the study vaccination they actually received.

In addition, the following Solicited Safety Set is defined for each injection separately. The First (Second) Injection Solicited Safety Set consists of all participants in the Solicited Safety Set who have received the first (second) study injection and have contributed any solicited AR data (eDiary) from the time of first (second) study injection through the following 6 days.

Participants will be analyzed according to the treatment group a subject received, rather than the vaccination group to which the participant was randomized. If a participant was randomized to placebo but received any dose of mRNA-1273 vaccine at any injection, the participants will be included in the mRNA-1273 group in the Solicited Safety Set.

5.7. Safety Set

The Safety Set consists of all randomized participants who received at least one dose of IP. The Safety Set will be used for all analysis of safety except for the solicited ARs. Participants will be included in the vaccination group corresponding to the IP they actually received. For a participant who was randomized to placebo but received any dose of mRNA-1273 at any injection, the participant will be included in the mRNA-1273 group in the Safety Set.

6. Statistical Analysis

6.1. General Considerations

The Schedule of Events is provided in the protocol Table 16-19.

Continuous variables will be summarized using the following descriptive summary statistics: the number of subjects (n), mean, standard deviation (SD), median, minimum (min), and maximum (max).

Categorical variables will be summarized using counts and percentages.

Baseline value, unless specified otherwise, is defined as the most recent non-missing measurement (scheduled or unscheduled) collected before the first dose of IP.

For the summary statistics of all numerical variables unless otherwise specified, the display precision will follow programming standards. Please see [Appendix A](#) for variable display standards.

When count data are presented, the percentage will be suppressed when the count is zero in order to draw attention to the non-zero counts. A row denoted “Missing” will be included in count tabulations where specified on the shells to account for dropouts and missing values. The denominator for all percentages will be the number of subjects in that baseline SARS-CoV-2 serostatus and treatment group within the analysis set of interest, unless otherwise specified.

Baseline SARS-CoV-2 status is determined by using virologic and serologic evidence of SARS-CoV-2 infection on or before Day 1.

Positive SARS-CoV-2 status at Baseline is defined as a positive RT-PCR test for SARS-CoV-2, and/or a positive serology test based on bAb specific to SARS-CoV-2 nucleocapsid (as measured by Roche Elecsys Anti-SARS-CoV-2 assay) on or before Day 1.

Negative status at Baseline is defined as a negative RT-PCR test for SARS-CoV-2 and a negative serology test (as measured by Roche Elecsys Anti-SARS-CoV-2 assay) at Day 1.

The baseline SARS-CoV-2 status is defined as missing for subjects with both tests missing, or with one test missing and one test negative.

Subjects with negative Baseline SARS-CoV-2 status will be included in the mITT population; subjects with positive or missing baseline SARS-CoV-2 status will be excluded from the mITT and PP population.

Age: unless otherwise specified, age is calculated as the age at screening. In subgroup analyses on age, age at screening will be used for derivation of age group.

Study day relative to the first injection will be calculated as below:

- a) study day prior to the first injection will be calculated as: date of assessment/event – date of the first injection;
- b) study day on or after the date of the first injection will be calculated as: date of assessment/event – date of the first injection + 1;

Study day relative to the most recent injection will be calculated as below:

- a) study day prior to the first injection will be calculated as: date of assessment/event – date of the first injection;
- b) study day on or after the date of the first injection but before the second injection (if applicable) will be calculated as: date of assessment/event – date of the first injection + 1;

- c) study day on or after the date of the second injection will be calculated as: date of assessment/event – date of the second injection + 1; if study day is on the same day as the second injection, date and time will be compared with the second injection date and time. If it is prior to the second injection, then study day is calculated as b); If it is after the second injection or the time is missing or not available then study day is calculated as: date of assessment/event – date of the second injection + 1.

Unscheduled visits: Unscheduled visit measurements will be included in analysis as follows:

- In scheduled visit windows per specified visit windowing rules.
- In the derivation of baseline measurements.
- In the derivation of maximum/minimum values after 1st dose and maximum/minimum change from baseline values for safety analyses.
- In individual subject data listings as appropriate.

Visit windowing rules: The analysis visit windows for protocol-defined visits are provided in [Appendix B](#).

Incomplete/missing data:

- Imputation rules for missing dates of prior/concomitant medications, non-study vaccinations and procedures are provided in [Appendix C](#).
- Imputation rules for missing AE dates are provided in [Appendix D](#).
- If the laboratory results are reported as below the LLOQ (e.g. < 0.1), the numeric values will be substituted by $0.5 \times \text{LLOQ}$ in the summary when treating the results as continuous variables. If the laboratory results are reported as greater than the ULOQ (e.g. > 3000), the numeric values will be substituted by ULOQ in the summary statistics for continuous variable.
- Other incomplete/missing data will not be imputed, unless specified otherwise.

Treatment groups

The following treatment groups will be used for summary purposes in Part A:

- mRNA-1273
- Placebo

If a subject received any dose of mRNA-1273 at any injection, regardless of the treatment group the subject was randomized to, the subject will be included to mRNA-1273 100 µg group as the actual treatment group received for safety analyses.

All analyses and data summaries/displays for disposition, baseline demographics and characteristics will be provided by Baseline SARS-CoV-2 Status (negative, positive, and overall) and treatment group unless otherwise specified. All analyses and data summaries/display for efficacy will be provided by treatment group using appropriate analysis population unless otherwise specified.

Analysis Periods

The following analysis periods and treatment groups will be used for efficacy analyses for the blinded phase (Part A):

Part A Group	Description	Blinded/Part A Analysis Period for Efficacy
mRNA-1273	Participants randomized to mRNA-1273 in the Blinded Phase	From randomization to earlier date of Participant Decision Visit (PDV)/unblinding, study discontinuation, study completion, death, or data cutoff date for efficacy)
Placebo	Participants randomized to Placebo in the Blinded Phase	

The analysis period and treatment groups of the blinded phase (Part A) for Safety analyses is summarized below:

Part A Group	Description	Blinded/Part A Analysis Period for Safety
--------------	-------------	---

mRNA-1273	Participants received at least one dose of mRNA-1273 in the Blinded Phase	From the first dose of study IP to the earlier date of (study discontinuation, study completion, death, data cutoff for safety, PDV/unblinding) for those who did not receive study IP in Part B. For participants received study IP in Part B, from the first dose of study IP in study to the earlier date of (data cutoff for safety, or 1st dose of study IP in Part B)
Placebo	Participants only received Placebo in the Blinded Phase	

The above analysis period for safety analysis in Part A is also referred to as Overall Period in Part A. For Part A, up to 28 days after any vaccination, starts at the day of each vaccination and continue through the earliest date of (the day of each vaccination and 27 subsequent days, next vaccination [if applicable]), will be used as the primary analysis period for safety analyses including unsolicited AE, except for solicited AR, unless specified otherwise.

Part B

Considering Part B/unblinded phase of the study, the following analysis periods may be used. SAP Part B will provide more details, and if the definition for Part B in SAP Part B differs from that described in this SAP, SAP Part B will prevail.

The following analysis period and treatment groups for Efficacy of the unblinded phase (Part B) may be used:

Part B Cohort	Description	Part B Analysis Period for Efficacy
mRNA-1273	Participants randomized to mRNA-1273 in the Blinded Phase	From PDV/unblinding to earlier date (data cutoff date for efficacy, last observed in Study) where last observed is earlier of (study discontinuation, study completion, death)
Placebo	Participants randomized to Placebo in the Blinded Phase and did not receive mRNA-1273 in Part B	
Placebo-mRNA-1273	Participants randomized to Placebo in the Blinded phase and received mRNA-1273 in Part B	

The following analysis period of the unblinded phase (Part B) and treatment groups for Safety analysis of the unblinded phase (Part B) may be used:

Part B Cohort	Description	Part B Analysis Period for Safety
mRNA-1273	Participants received at least one dose of mRNA-1273 in the Blinded Phase	From PDV/unblinding to earlier date of (data cutoff date for safety, last observed in Study). If a participant received mRNA-1273 in Part B, from 1 st date of study IP in Part B to earlier date of (data cutoff date for safety, last observed in Study).
Placebo	Participants only received Placebo in the Blinded Phase and did not receive mRNA-1273 in Part B	From PDV/unblinding to earlier date of (data cutoff date for safety, last observed in Study)
Placebo-mRNA-1273	Participants only received Placebo in the Blinded phase and received mRNA-1273 in Part B	From first dose of mRNA-1273 in Part B to earlier date of (data cutoff date for safety, last observed in Study)

All analyses will be conducted using SAS Version 9.4 or higher unless otherwise specified.

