Participants who are unblinded, received placebo, are eligible, and request to receive mRNA-1273 (as long as investigational vaccine is available) (Figure 2), will have the following clinic visits as shown in the Supplemental SoE (Table 21):

- Open-label Dose 1 (OL-D1): To occur at the PDV or at a scheduled subsequent visit.
- Open-label Dose 2 (OL-D29): To occur 28 days after Dose 1 on OL-D1.
- Open-label Clinic Visit (OL-D57): To occur 1 month after Dose 2 on OL-D29.

- And in addition, continue to comply with the Original Study SoEs ([Table 16](#), [Table 17](#), [Table 18](#), and [Table 19](#)) as applicable.
- Participants who are unblinded, and received ONLY 1 dose of mRNA-1273 may be eligible to receive 1 more dose of mRNA-1273 if: They had a dosing error in Part A of the study that resulted in 1 dose of mRNA-1273 and 1 dose of placebo being administered.
- They did not have an AE that contraindicated the second dose of mRNA-1273 in Part A of the study.
- They did not withdraw consent in Part A of the study.
- They did not complete their second dose in Part A of the study for reasons other than the above.

If participants are eligible, and request to receive mRNA-1273 ([Figure 2](#)) will proceed to have the following clinic visits as shown in the Modified Supplemental SoEs ([Table 22](#)):

- Their second dose on OL-D1: To occur at the PDV or at a scheduled subsequent visit.
- Open-label Clinic Visit (OL-D29): To occur 1 month after Dose 2 on OL-D1.
- And in addition, continue to comply with the Original Study SoEs ([Table 16](#), [Table 17](#), [Table 18](#), and [Table 19](#)) as applicable.

All participants remain on their original SoE to complete 24 months of follow-up after Dose 2; study participants who enter the Supplemental/Modified Supplemental SoE as described above do so in addition to their original SoE. Accordingly, all study participants will complete the full study follow-up to 24 months after the second dose of their original inoculation (mRNA-1273 or placebo) or 25 months after the first dose if the second dose is missed.

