Note: In accordance with FDA Guidance on Conduct of Clinical Trials of Medical Products during the COVID-19 Pandemic (DHHS 2020a), investigators may convert study site visits to telemedicine visits with the approval of the Sponsor. All scheduled study visits should be completed within the respective visit windows. If the participant is not able to come on-site for a study site visit as a result of the COVID-19 pandemic (self-quarantine or disruption of study site activities following business continuity plans and/or local government mandates for “stay at home” or “shelter in place”), a safety call to the participant should be made in place of the study site visit. The safety call should encompass all scheduled visit assessments that can be completed remotely, such as assessment for AEs and

concomitant medications (eg, as defined in scheduled biweekly safety phone calls). Home visits will be permitted for all non-dosing visits except for Screening if a participant cannot come to the study site as a result of the COVID-19 pandemic.

4. The Day 0 and OL-D1 visit may be performed on 2 separate visits.
5. Symptom-directed physical examination will be performed at the PDV and on OL-D29. On each dosing day before injection, the arm receiving the injection should be examined and the associated lymph nodes should be evaluated. Any clinically significant finding identified during a study visit should be reported as an MAAE. Vital signs are to be collected pre- and post-dosing on days of injection (OL-D1 and OL-D29). Participants who are febrile (body temperature $\geq 38.0^{\circ}\text{C}/100.4^{\circ}\text{F}$) before dosing (OL-D1 and OL-D29) must be rescheduled within the relevant window period to receive the injection. Afebrile participants with minor illnesses can be enrolled at the discretion of the investigator.
6. Pregnancy test at the PDV and OL-D29 will be a point-of-care urine test. At the discretion of the investigator, a pregnancy test either via blood or point-of-care urine test can be performed. Follicle-stimulating hormone level may be measured to confirm menopausal status at the discretion of the investigator.

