6.6.1. Unsolicited Treatment-emergent Adverse Events

A treatment-emergent AE (TEAE) is defined as any event occurring during the study not present before exposure to the IP or any event already present that worsens after exposure to study vaccine. Worsening of a pre-existing condition after vaccination will be reported as a new AE.

Adverse events will also be evaluated by the investigator for the coexistence of MAAE which is defined as an AE that leads to an unscheduled visit to a healthcare practitioner.

Unsolicited AEs will be coded by PT and SOC using MedDRA and summarized by vaccination group.

Unsolicited AEs will be collected for up to 28 days after each IP dose; SAEs, MAAEs, AEs leading to withdrawal will be collected throughout the study. Analyses of unsolicited AE will be provided for up to 28 days after any vaccination unless otherwise specified; and select analyses of unsolicited AE will be provided for Surveillance stage, and overall stage ([Section 6.1](#)).

All summary tables (except for the overall summary of AEs) for unsolicited AEs will be presented by SOC and PT or by PT only for TEAEs with counts of subjects included. SOC will be displayed in internationally agreed order. PT will be displayed in descending order of frequency of mRNA-1273 and then alphabetically within SOC. When summarizing the number and percentage of subjects with an event, subjects with multiple occurrences of the same AE or a continuing AE will be counted once. Only the maximum severity level will be presented in the severity summaries, and the strongest relationship level will be presented in the relationship summaries.

Unsolicited TEAE will be summarized up to 28 days after any injection. Unsolicited TEAEs may be summarized throughout the study and will be referred to as Overall stage (Part A), defined as from the first dose of study IP to the earlier date of (study discontinuation, study completion, death, data cutoff for safety, PDV/unblinding) for those who did not receive study IP in Part B; or from the first dose of study IP to the earlier date of (study discontinuation, study completion, death, data cutoff for safety, or 1st dose of study IP in Part B) for those who received study IP in Part B.

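### The Part A Overall safety period runs past PDV/unblinding only for participants dosed in Part B, so any wait for open-label Dose 1 adds unblinded follow-up mainly to placebo

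*SAP*

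**What the plan says.** Section 6.1 of the Part A SAP gives the safety period of the blinded phase two possible end dates. The first branch stops at the earliest of several dates, the last two being "data cutoff for safety, PDV/unblinding) for those who did not receive study IP in Part B". The second branch, for participants dosed in Part B, runs "to the earlier date of (data cutoff for safety, or 1st dose of study IP in Part B"), so the PDV does not end it. This period "is also referred to as Overall Period in Part A". Section 6.6.1 repeats the split for the Overall stage, ending at "data cutoff for safety, or 1st dose of study IP in Part B) for those who received study IP in Part B".

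The same section 6.1 defines a separate window of up to 28 days after each vaccination, which "will be used as the primary analysis period for safety analyses including unsolicited AE, except for solicited AR, unless specified otherwise".

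On timing, Protocol 4.1.2 states for placebo crossovers: "Open-label Dose 1 (OL-D1): To occur at the PDV or at a scheduled subsequent visit". A footnote to Table 21 in Protocol Appendix 1 adds: "The Day 0 and OL-D1 visit may be performed on 2 separate visits".

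The efficacy period in section 6.1 has one end rule for both arms, and that rule includes PDV/unblinding.

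**The concern.** Part B dosing is open to placebo recipients and to participants who had only one dose of mRNA-1273 (Protocol 4.1.2). Two-dose vaccine recipients therefore always stop at the PDV, while placebo recipients who cross over continue until they are injected. If that injection comes later, the interval has three features:

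- It follows unblinding, since crossover requires it.
- It falls mainly in one arm.
- It is counted in tables meant to describe the blinded comparison.

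Section 6.6.1 bases percentages on the number of participants in the Safety Set, and its rate ratio is a ratio of those percentages. Neither allows for unequal follow-up.

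At stake is the Overall Stage comparison of SAEs, MAAEs and AEs leading to discontinuation. SAP 3.1.2 makes SAEs, MAAEs and AEs leading to withdrawal primary safety endpoints over the whole study, which a 28-day window cannot cover. Confirmed COVID-19 is recorded as an MAAE (Protocol 8.1.2), so added placebo time also adds COVID-19 MAAEs.

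**Working it through.** The documents state no gap between PDV and OL-D1 and no mean Part A safety follow-up, so there is no planned figure to reproduce. The check compares the rules and then illustrates their size.

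**Step 1. Who falls under which end date**

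| Participant | Part A safety period ends (if no earlier stop applies) |
|---|---|
| mRNA-1273, two doses, none in Part B | PDV/unblinding |
| mRNA-1273, one dose, second in Part B | OL-D1 |
| Placebo, not crossing over | PDV/unblinding |
| Placebo, crossing over | OL-D1 |

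The branch depends on Part B dosing, not on arm. The imbalance arises because crossing over is mainly a placebo event.

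**Step 2. Which tables use the period.** SAP 6.6.1.1 plans the overview of unsolicited TEAEs for the Overall Stage as well as for 28 days. SAP 6.6.1.2 plans Overall Stage tables by system organ class and preferred term for all unsolicited TEAEs, SAEs, treatment-related SAEs, MAAEs and TEAEs leading to study discontinuation. Under SAP 6.6.1, routine unsolicited AEs are collected only up to 28 days after each dose. Beyond that, the extra interval can add only SAEs, MAAEs and AEs leading to withdrawal.

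**Step 3. Extra follow-up per crossover participant.** Let T be follow-up to the PDV (assumed 150 days) and g the gap from PDV to OL-D1 (assumed). Extra follow-up = g/T:

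- g = 0: 0/150 = 0%
- g = 7: 7/150 = 4.7%
- g = 14: 14/150 = 9.3%
- g = 28: 28/150 = 18.7%

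**Step 4. Arm level, under equal true hazards.** Let f be the share of placebo recipients who cross over (assumed) and p the percentage with an event by T in the vaccine arm (assumed 1%). Then:

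- Extra placebo person-time = f × g/T
- λ = −ln(1 − p)/T
- Apparent vaccine/placebo ratio = p / [(1 − f)p + f(1 − exp(−λ(T + g)))]

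Example with T = 150, g = 28, f = 0.9:

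- λ = 0.01005/150 = 0.0000670 per day
- Crossover participants: 1 − exp(−0.0000670 × 178) = 0.01186
- Placebo arm: 0.1 × 0.01 + 0.9 × 0.01186 = 0.01167
- Ratio: 0.01/0.01167 = 0.86

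| Gap (days) | Extra placebo person-time, T = 150, f = 0.9 | Ratio | Range over T = 90 to 180, f = 0.5 to 1.0 |
|---|---|---|---|
| 0 | 0% | 1.00 | 0%; 1.00 |
| 7 | 4.2% | 0.96 | 1.9% to 7.8%; 0.98 to 0.93 |
| 14 | 8.4% | 0.92 | 3.9% to 15.6%; 0.96 to 0.87 |
| 28 | 16.8% | 0.86 | 7.8% to 31.1%; 0.93 to 0.76 |

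With a common end date, g no longer enters and the ratio is 1.00.

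**The case against.** The rule is not written by arm. Dosing at the PDV is the first option named in Protocol 4.1.2, and Table 21 places PDV and OL-D1 under one study-day heading. For participants injected that day there is no extra time. The rule also leaves no interval unreported: under SAP 6.1 the Part B safety period for crossovers starts only at the first open-label dose, and until then they have received only placebo. That is a defensible reason, although the SAP does not state it. All of this stands, but it does not make the follow-up comparable when the injection is later, and no limit on the gap is given.

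The primary safety window is unaffected, and section 6.6.1 calls the rate ratio descriptive. Both are true. However, the 28-day window does not serve the whole-study endpoints.

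The end date also depends on a later event. A placebo recipient whose event after the PDV prevents dosing reverts to the PDV cut-off, which would partly offset the effect. Conversely, Protocol 7.1 delays dosing for fever, acute infection or diagnosed COVID-19, which lengthens the gap in people who are having events. The illustration ignores both.

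A reader might infer that placebo percentages are certainly inflated, or that all unsolicited AEs are. The documents do not support either reading. They give no gap distribution, and routine unsolicited AE collection stops 28 days after a dose.

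**Conclusion.** The point holds for the Overall Period/Stage only. Where OL-D1 follows the PDV, the plan counts unblinded time that falls mainly on placebo, with no person-time adjustment. The expected direction understates a vaccine excess in SAEs, MAAEs and AEs leading to discontinuation. A reader might go further and conclude that the primary safety analysis is biased or that the SAP sets end dates by arm. It does neither: the 28-day window does not use this rule, and the branch turns on Part B dosing.

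The size is conditional. It is zero for same-day dosing. With an assumed 150 days of follow-up and gaps of 7 to 28 days, it is 5% to 19% more follow-up per crossover participant. With 90% crossing over, the gap unrelated to events and a constant hazard, it is 4% to 17% at arm level. The actual gap has to come from the trial data. This should be corrected, but it does not threaten the primary safety window.

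**What to change.** For Overall Stage between-group comparisons, end every participant's follow-up at the earliest of PDV/unblinding, study discontinuation, study completion, death or safety cutoff, matching the efficacy period. Report events from PDV to OL-D1 in their own row or interval, with the distribution of the gap. They should not be moved into the Placebo-mRNA-1273 Part B cohort: its safety period in SAP 6.1 and Table 5 starts at the first open-label dose, so they would either drop out or appear as events after vaccination. Table 1 of the Part B/C SAP lists both PDV/unblinding and first Part B dose as starts without assigning them to cohorts, so the new interval should be defined explicitly. The alternative is to keep the present dates and add exposure-adjusted rates.

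Sections 6.1 and 6.6.1 should also be aligned: for participants dosed in Part B, 6.6.1 lists discontinuation, completion and death as end dates and 6.1 omits them.

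The cost is one more interval to tabulate. The Part B/C SAP treats the Part A analyses as completed, so this would be a supplementary re-tabulation from dates already held.
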